## **8.7. Emergency Unblinding**

Unblinding of treatment assignment for a participant may be necessary due to a medical emergency, or any other significant medical event, when a treatment decision for that medical emergency/significant event is contingent upon knowing the participant's treatment assignment. Any participant who becomes RT-PCR positive during the study is eligible to receive post-infection treatment with casirivimab+imdevimab without unblinding.

If unblinding is required:

- The investigator will make the decision to unblind the treatment assignment, following consultation with the Sponsor or the global Principal Investigator
- Only the affected participant will be unblinded
- Unblinding is performed using the IWRS, which will notify the Sponsor. The designated study pharmacist(s)/designee at the study site will provide the treatment assignment to the investigator. If the study pharmacist(s)/designee is not available, the investigator for the site will unblind the participant
- If the IWRS is unavailable, the investigator will ask the unblinded study pharmacist(s)/designee to perform manual unblinding. All manual unblinding procedure will be adequately documented, including the reason why the IWRS was not used
- The investigator will notify the Sponsor and/or designee as soon as possible after unblinding the participant

Treatment assignment is not to be provided to site personnel, other than the unblinded study pharmacist (when applicable), at any time during the conduct of the study, except in the case of a true emergency and when a treatment decision is contingent on knowing the participant's treatment assignment. In the event that there is no study pharmacist, the individual at the site fulfilling that role will be the only unblinded member of the site personnel.

## **8.8. Treatment Logistics and Accountability**

### **8.8.1. Packaging, Labeling, and Storage**

A medication numbering system will be used to label unblinded investigational study drug. Lists linking medication numbers with product lot numbers will be maintained by the groups (or companies) responsible for study drug packaging. In order to maintain the blind, these lists will not be accessible to individuals involved in study conduct.

The unblinded pharmacist will prepare the unblinded investigational product and dispense it in a blinded manner to the blinded study staff for administration to the participant.

Study drug will be stored at the site at a temperature of 2°C to 8°C. Storage instructions will be provided in the pharmacy manual.

### **8.8.2. Supply and Disposition of Treatments**

Study drug will be shipped at a temperature of 2°C to 8°C to the investigator or designee at regular intervals or as needed during the study. At specified time points during the study (eg, interim site monitoring visits), at the site close-out visit, and following drug reconciliation and documentation by the site monitor, all opened and unopened study drug will be destroyed at the site with approval by the Sponsor or returned to the Sponsor or designee.

### **8.8.3. Treatment Accountability**

All drug accountability records must be kept current.

The investigator must be able to account for all opened and unopened study drug. These records should contain the dates, quantity, and study medication:

- Dispensed to each participant
- Returned from each participant (if applicable), and
- Disposed of at the site or returned to the Sponsor or designee.

All accountability records must be made available for inspection by the Sponsor and regulatory agency inspectors; photocopies must be provided to the Sponsor at the conclusion of the study.

### **8.8.4. Treatment Compliance**

All drug compliance records must be kept current and made available for inspection by the Sponsor and regulatory agency inspectors.

## **8.9. Concomitant Medications and Procedures**

Any treatment or procedure administered from the time of the first dose of study drug to the final study visit will be recorded as concomitant medication or concomitant procedure. This includes medications or procedures that were started before the study and are ongoing during the study.

### **8.9.1. Prohibited Medications**

The following concomitant medications are prohibited and may result in permanent discontinuation of study drug:

- Investigational, authorized, or approved COVID-19 vaccines within 90 days of the last dose of study drug (or per current CDC recommendations) ([CDC, 2021](#))
- Investigational or approved passive antibodies for SARS-CoV-2 infection (eg, convalescent plasma or sera, monoclonal antibodies, hyperimmune globulin), remdesivir, or other anti-SARS-CoV-2 agents when used as prophylaxis

### **8.9.2. Permitted Medications**

Other than the prohibited medications listed in Section [8.9.1](#), concomitant medications are permitted during the study. If there is any question regarding whether a concomitant medication may be used during the study, the study site should contact the Sponsor medical monitor.

## **9. STUDY SCHEDULE OF EVENTS AND PROCEDURES**

### **9.1. Schedule of Events**

In light of the public health emergency related to COVID-19, the continuity of clinical study conduct and oversight may require implementation of temporary or alternative mechanisms. Examples of such mechanisms may include, but are not limited to, any of the following: phone contact, virtual visits, telemedicine visits, online meetings, non-invasive remote monitoring devices, use of local clinic or laboratory locations, and home visits by skilled staff. Additionally, no waivers to deviate from protocol enrollment criteria due to COVID-19 will be granted. All temporary mechanisms utilized, and deviations from planned study procedures are to be documented as being related to COVID-19 and will remain in effect only for the duration of the public health emergency.

Study assessments and procedures are presented by study period and visit in [Table 1](#).

**Table 1: Schedule of Events (No Longer Applicable as of Protocol Amendment 2)**

Study Day	Screening/Baseline 				Efficacy Assessment Period 					Follow-Up Period 			Confirmatory Visit, Suspected COVID-19 	Post-Infection Treatment Visit, Lab-Confirmed Infection 	ET			
	-14 to 1		1		8 	29	57	85	113	141	169	197 (FU 1)	225 (FU 2)	253 (EOS)				
	Screen	Pre-Dose	Dose	Post-Dose														
Window (Day)					±3	±7	±7	±7	±7	±7	±7	±7	±14	±14	±14			
Screening/Baseline																		
Informed consent	X																	
Inclusion/exclusion	X																	
Medical history	X																	
Demographics	X																	
Weight and height	X																	
Locally-acceptable sample for SARS-CoV-2 RT-PCR (local) 	X																	
NP swab sample for SARS-CoV-2 RT-qPCR (central) 		X																
Randomization		X																
Treatment																		
Study drug administration 			X		X	X	X	X	X									
Safety																		
Vital signs 		X		X		X	X	X	X	X	X							
Treatment-emergent grade ≥3 AEs 			X	X	X	X	X	X	X	X	X	X	X			X		
Treatment-emergent AEs leading to study drug discontinuation 			X	X	X	X	X	X	X	X	X	X	X			X		
Treatment-emergent SAEs 			X	X	X	X	X	X	X	X	X	X	X			X		
Treatment-emergent grade ≥2 hypersensitivity reactions 			X	X	X	X	X	X	X							X		
Treatment-emergent grade ≥3 ISRs 			X	X	X	X	X	X	X							X		
Concomitant medications and procedures	X			X	X	X	X	X	X	X	X	X	X			X		
Pregnancy test, blood or urine (WOCBP only)	X				X		X		X									
Pregnancy status											X		X			X		
Vital status				X							X	X	X			X		
Safety information (newborns of study participants)													X			X		
Efficacy																		
Clinician assessment of COVID-19 signs and symptoms			X		X	X	X	X	X	X	X	X	X			X 		
Central Laboratory Pharmacodynamic/Biomarker Testing																		
Serum for central anti-SARS-CoV-2 serological assays		X 																
Serum for exploratory research		X 									X							
Plasma for exploratory research		X 								X								

Study Day	Screening/Baseline 				Efficacy Assessment Period 					Follow-Up Period 			Confirmatory Visit, Suspected COVID-19 	Post-Infection Treatment Visit, Lab-Confirmed Infection 	ET			
	-14 to 1		1		8 	29	57	85	113	141	169	197 (FU 1)	225 (FU 2)	253 (EOS)				
	Screen	Pre-Dose	Dose	Post-Dose														
Window (Day)					±3	±7	±7	±7	±7	±7	±7	±7	±14	±14	±14			
Pharmacokinetics and Immunogenicity Sampling (first 600 enrollees at participating sites)																		
Serum for drug concentration (PK) 			X 		X	X		X			X		X					
Serum for immunogenicity (ADA) 			X 		X						X							
Participants with suspected COVID-19 only																		
Clinician assessment of COVID-19 signs/symptoms														X				
Comprehensive vital sign assessment														X	X 			
Treatment-emergent grade ≥3 AEs														X	X			
Treatment-emergent SAEs 														X	X			
Concomitant medications and procedures														X	X			
If confirmed symptomatic	Locally-acceptable sample for SARS-CoV-2 RT-PCR (local)													X				
	NP swab for SARS-CoV-2 RT-qPCR (central)													X				
If SARS-CoV-2 RT-PCR is positive	Post-infection treatment														X			
	Clinician assessment of COVID-19 signs/symptoms												Every 7 (±1) days until 2 consecutive negative RT-qPCR results 					
	NP swab for SARS-CoV-2 RT-qPCR (central)												X					
	COVID-19-related MAV details				X	X	X	X	X	X	X	X	X	X				

ADA, anti-drug antibodies; AE, adverse event; EOS, end of study; FU, follow up; ISR, injection-site reactions; MAV, medically-attended visit; NP, nasopharyngeal; PK, pharmacokinetics; SAE, serious adverse event; RT-PCR, reverse transcription polymerase chain reaction; RT-qPCR, quantitative reverse transcription polymerase chain reaction; SARS-CoV-2, severe acute respiratory syndrome coronavirus 2; WOCBP, women of childbearing potential.

**Table 2: Schedule of Events for Study Close-Out (Protocol Amendment 2; Applies to All Enrolled Participants)**

Study Visit	Dose Visit	Optional Confirmatory Visit(s), Suspected COVID-19	End-of-Study Follow-Up Visit (Telephone)
Timing of Visit	28 Days After the Most Recent Dose	Within 48 Hours of Symptom Onset, if Feasible	85 Days After the Most Recent Dose
Window (Days)	±7	-	±14
Informed consent	X 		
Optional study drug administration 	X		
Vital signs 	X		
Treatment-emergent AEs considered by the investigator to be unrelated to baseline conditions and unrelated to treatments for baseline conditions 	X		X
Treatment-emergent AEs leading to study drug discontinuation 	X		X
Treatment-emergent SAEs 	X		X
Treatment-emergent grade ≥2 hypersensitivity reactions 	X		
Treatment-emergent grade ≥3 injection site reactions (ISRs) 	X		
Concomitant medications and procedures	X		X
Pregnancy status			X
Vital status			X
Safety information (newborns of study participants)			X
Participants with suspected COVID-19 only (optional)			
Clinician assessment of COVID-19 signs/symptoms 		X 	
Comprehensive vital sign assessment 		X 	
Treatment-emergent AEs considered by the investigator to be unrelated to baseline conditions and unrelated to treatments for baseline conditions 		X 	
Treatment-emergent SAEs 		X 	
Concomitant medications and procedures		X 	
If confirmed symptomatic:	Locally-acceptable sample for SARS-CoV-2 RT-PCR (local) 	X 	
	NP swab for SARS-CoV-2 RT-qPCR (central) 	X 	
If SARS-CoV-2 RT-PCR is positive:	Clinician assessment of COVID-19 signs/symptoms	Every 7 (±1) days until 2 consecutive negative RT-qPCR results 	
	NP swab for SARS-CoV-2 RT-qPCR (central)		
	COVID-19-related MAV details		

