## AMENDMENT HISTORY

### Amendment 2

The primary purpose of this amendment is to close the study. The procedures described in this amendment supersede those of the original protocol and site memorandum.

Description of Change	Brief Rationale	Section(s)

Added a new section with procedures specifying the study closure process, which includes the following:
 
 
• Participants will be offered the option to receive a supplemental final dose of casirivimab+imdevimab 1200 mg SC
 
• All participants, including those who do not consent to receive the optional final dose, will have a follow-up (end-of-study) telephone visit approximately 3 months from their last dose of investigational drug (casirivimab+imdevimab or placebo) to monitor safety
 
• Participants with suspected COVID-19 may have an optional visit to evaluate signs and symptoms and to receive local and central laboratory testing for SARS-CoV-2
 
• For participants who are SARS-CoV-2 positive, additional weekly visits can optionally occur until 2 consecutive negative RT-qPCR tests are obtained
 
• Safety collection will be broadened from original protocol to include treatment-emergent AEs considered by the investigator to be unrelated to baseline conditions and unrelated to treatments for baseline conditions.
 
• Participants will be monitored for at least 60 minutes after receiving study drug
 
• Sites will ensure that an additional discussion about the potential risks and benefits to the participant and fetus is discussed as part of re-consent for participants who become pregnant during the study
 
• A modified statistical analysis plan has been summarized for participants who have already enrolled in the study
 
	
To provide guidance to US sites regarding study close-out procedures.
	
Protocol Amendment 2 Procedures  Table 2 Schedule of Events for Study Close-Out (Applies to All Enrolled Participants Per Protocol Amendment 2)  Section 9.1.2 Footnotes for the Schedule of Events (Protocol Amendment 2)

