## Site Memorandum

This section describes changes to study conduct that were implemented by a site memorandum issued on 21 October 2021.

Original Protocol	Change / Additional Measures
No Scheduled Safety Labs	Measure absolute neutrophil count, platelet count, hemoglobin, ALT, AST, total bilirubin, and creatinine at the baseline visit as well as study visits days 29, 85 and 169
Monitor for 15 minutes after first dose	Monitor for 60 minutes after administration of study drug
Report treatment emergent adverse events (TEAEs) that are grade $\geq 3$ in severity	Report all clinical and laboratory TEAEs that are not related to the patient's underlying (non-COVID) disease and/or not related to treatments for the underlying conditions

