### 4.2. Secondary Endpoints

The secondary endpoints are:

- Proportion of participants with grade  $\geq 3$  treatment-emergent adverse events (TEAEs), during the EAP and follow-up period
- Proportion of participants with TEAEs leading to study drug discontinuation, during the EAP and follow-up period
- Proportion of participants with treatment-emergent serious adverse events (SAEs) during the EAP and follow-up period
- Incidence of adverse events of special interest (AESIs) during the EAP
- Concentration of each mAb (as applicable to the treatment arm) over time
- Incidence and titer of anti-drug antibodies (ADA), and incidence of neutralizing antibodies (NAb) to each mAb (as applicable to the treatment arm) over time

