#### **9.1.2. Footnotes for the Schedule of Events (Protocol Amendment 2)**

1. Approximately 85 days after the final dose of study drug (ie, the optional final dose of casirivimab+imdevimab defined in protocol amendment 2, or the final assigned casirivimab+imdevimab or placebo dose for participants who do not receive the optional dose).
2. Informed consent may be obtained at the dosing visit, or at any time prior to the visit via remote consent (if available and allowable at the study site).
3. Applicable to participants who consent to receive a final optional dose of 1200 mg SC casirivimab+imdevimab. The optional dose may be administered to all participants regardless of treatment assignment at randomization. However, participants will not be eligible to receive this dose if they have already received casirivimab+imdevimab as post-infection treatment. The dose will be recorded.
4. Vital signs (defined in Section [9.2.5.1](#)) will be collected before study drug administration and at least 60 minutes after completion of study drug administration.
5. Refer to Section [10.1](#) for AE monitoring and reporting guidelines.

6. Note that all assessments and procedures related to participants with suspected COVID-19 are optional for both the study site and the study participant. Refer to [Protocol Amendment 2 Procedures](#) for additional information.
7. Clinician assessment of sign or symptoms may occur remotely. If remote assessment is performed, a confirmatory site visit for laboratory testing of SARS-CoV-2 can optionally occur after a clinician deems that the signs or symptoms are related to COVID-19.
8. Comprehensive vital sign assessment includes standard vital sign assessment (defined in Section [9.2.5.1](#)), SpO2, and respiratory rate.
9. Note that samples for local and central laboratory testing of SARS-CoV-2 may be collected on the same day; the results of local testing are not required prior to sample collection for central testing.

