## 10. SAFETY EVALUATION AND REPORTING

### 10.1. Recording and Reporting Adverse Events

This study will collect and record the following targeted TEAEs:

- Treatment-emergent grade  $\geq 3$  AEs
- Treatment-emergent AEs leading to study drug discontinuation
- Treatment-emergent SAEs
- Treatment-emergent grade  $\geq 2$  hypersensitivity reactions
- Treatment-emergent grade  $\geq 3$  injection-site reactions

*Note: throughout Section 10, the term “AE” refers to the targeted list above.*

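### Protocol Table 2 does not require every grade ≥3 TEAE to be collected, while Section 10.1 and the first secondary safety endpoint still do

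*Protocol*

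**What the plan says.** The first secondary endpoint in Protocol 4.2 is the proportion of participants with grade ≥3 "treatment-emergent adverse events (TEAEs), during the EAP and follow-up period". SAP 5.8 item 1 repeats it. Neither limits it by cause.

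Table 1 collected "Treatment-emergent grade ≥3 AEs" at the scheduled visits and at the suspected-COVID visit. Its title now reads "Schedule of Events (No Longer Applicable as of Protocol Amendment 2". Table 2, which replaces it for all enrolled participants, has no such row. Its first AE row is "Treatment-emergent AEs considered by the investigator to be unrelated to baseline conditions and unrelated to treatments for baseline conditions". The other rows are AEs leading to study drug discontinuation, SAEs, grade ≥2 hypersensitivity reactions and grade ≥3 injection-site reactions. The suspected-COVID column has only the attribution row and the SAE row.

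The site memorandum of 21 October 2021 had already set the grade ≥3 rule in its original-protocol column against a new instruction: "Report all clinical and laboratory TEAEs that are not related to the patient", continuing with the underlying disease and/or its treatments. SAP 1.1 (Safety Analyses) adopts that wording and ascribes it to Amendment 2.

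Other current text keeps the old rule. Footnote 5, attached to every AE row of Table 2, refers to Section 10.1 "for AE monitoring and reporting guidelines". Section 10.1 says "This study will collect and record the following targeted TEAEs" and puts grade ≥3 AEs first, with no condition on cause. Protocol 11.4.5.1 and SAP 4.6.1 carry the same list.

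**The concern.** Table 2 makes the recording of a severe event depend on the investigator's view of its cause. Participants are transplant recipients, people with haematologic malignancy, or people on immunosuppressants, so a severe event may well be put down to the baseline condition or its therapy. A site working from the visit table could leave such an event out and believe it had complied. The endpoint would then be a mixture: severe events judged unrelated, plus those attributed to baseline disease that happened to be serious, to stop study drug or to be AESIs.

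Safety is the main deliverable of this closed study. The Amendment 2 statistical text says all safety endpoints will be summarized, whereas selected efficacy, virology, PK and immunogenicity data only may be. SAP 1.2.4 lists modifications from the protocol and mentions only dropped exploratory efficacy endpoints, so a reader of the results would not be told which collection rule lies behind the grade ≥3 proportion.

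**Working it through.** The plan has no figure of its own to reproduce here. The check is a comparison of text, followed by one line of arithmetic.

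**1. The rules side by side**

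| Place | Which non-AESI TEAEs |
|---|---|
| Protocol 4.2; SAP 5.8 item 1 (endpoint) | All grade ≥3, any cause |
| Protocol 10.1 and 11.4.5.1; SAP 4.6.1 (collection) | All grade ≥3, any cause; SAEs; those leading to discontinuation |
| Site memorandum; SAP 1.1 (collection) | Any grade, if not related to underlying disease and/or its treatments |
| Protocol Table 2 (collection) | Any grade, if unrelated to baseline conditions and to their treatments; SAEs; those leading to discontinuation |

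**2. Is the missing row a slip?** The same exchange occurs in four places: the two columns of the memorandum; the scheduled-visit rows of Tables 1 and 2; the suspected-COVID rows of the same tables; and the note on recording symptoms. Section 9.2.4.2 ties that note to grade ≥3 TEAEs, while the Amendment 2 procedures tie it to events unrelated to baseline conditions. The exchange is consistent.

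**3. What falls outside Table 2.** A grade ≥3 TEAE has a row if it is (a) unrelated to baseline conditions and their treatments, (b) serious, (c) a cause of study drug discontinuation, or (d) a listed hypersensitivity or injection-site reaction. An event meeting none of (a) to (d) has no row: non-serious, attributed to baseline disease or its treatment, not leading to discontinuation, not an AESI. It still counts towards the endpoint in Protocol 4.2.

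**4. The connective matters.** Take an event attributed to the underlying disease but not to its treatment. Under Table 2 both conditions must hold, so it is outside the row. Under the memorandum and SAP 1.1, reading the connective as an or, it is inside, because it is not related to treatment. The attribution rule itself therefore has two versions.

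**5. Size per missed participant.** SAP 2.1 gives 66 randomized, about 16 to 17 per arm (66/4 = 16.5). If one participant's only grade ≥3 TEAE goes unrecorded, that arm's proportion falls by

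- 1/17 = 5.9 percentage points, or
- 1/16 = 6.25, about 6.3 percentage points.

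For k such participants the fall is k/17 to k/16. The documents give no value for k. The divisor is the randomized count; safety is analysed in the safety set, whose size is not stated.

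**The case against.** The strongest reply is that nothing was removed. Footnote 5 sends the site from each AE row of Table 2 to Section 10.1, where grade ≥3 AEs still head the list. The amendment history says "Safety collection will be broadened from original protocol" to include the new category, which reads as an addition. The memorandum's column heading also allows for additional measures. SAP 5.8.1 plans one overview of all TEAEs and another of those not related to underlying disease, which suggests that baseline-attributed events were expected in the database.

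Much of this stands, and it rules out the stronger conclusion that the endpoint has already been under-collected. It does not settle which rule governs. Section 10.1 omits the new attribution category, so it was evidently not updated. Amendment 2 says its procedures supersede the original protocol and the memorandum. The end-of-study call is limited to targeted AEs as set out in Table 2. The two overviews in SAP 5.8.1 could differ through SAEs alone.

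The exposed class is also narrow. Hospitalization and life-threatening consequences in the grade 3 and 4 descriptions overlap with the SAE criteria. Table 2 schedules no laboratory tests, isolated laboratory abnormalities are AEs only under the conditions in Section 10.1.1, and SAP 5.8.3 lists all local laboratory results. These points limit the likely number of missed events but do not bring it to zero.

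**Conclusion.** The documents contradict themselves on whether all grade ≥3 TEAEs must be collected, and the endpoint matches only one of the two rules. A site following Table 2 alone would under-collect it; a site following footnote 5 to Section 10.1 would not. Each participant missed would cost the arm about 6 percentage points (5.9 to 6.3, on randomized counts).

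A reader might infer more, and the documents do not support it:

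- **That data were lost.** This depends on what sites did, which is not recorded here.
- **That a particular number per arm was missed.** No rate is given, so only the per-participant figure can be stated.
- **That participants from before and after the change are pooled under different definitions.** Enrollment closed on 16 December 2021, but no first-enrolment date or count before the memorandum is given, so it is unknown whether participants span the change.

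The consequence is limited to descriptive reporting: no inferential claim depends on this proportion, and SAP 1 designates all endpoints exploratory. Its completeness still needs to be known before it is reported.

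**What to change.** If Table 2 can still be amended, add a row for treatment-emergent grade ≥3 AEs regardless of relationship to its three visit columns, in line with Sections 4.2 and 10.1. Keep the attribution row as an addition, and add that category to the lists in Sections 10.1 and 11.4.5.1 and SAP 4.6.1. Use one connective (and, or and/or) in Table 2, the memorandum text and SAP 1.1.

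The SAP was approved in June 2022, so collection may be finished. In that case:

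- Establish which rule sites actually applied.
- State in SAP 5.8 item 1 and SAP 1.2.4 which grade ≥3 TEAEs enter the proportion under that rule. Do not describe the endpoint as restricted unless sites are confirmed to have used the Table 2 rule; if they followed Section 10.1, such a statement would be false.
- Tabulate by collection rule only if participants span the change.

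The cost is a few more non-serious AE entries among 66 participants, or a check with sites and two SAP sentences.
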